3.6 Coronavirus Disease 2019

Mechanisms to record information on the potential impact of the COVID-19 pandemic on data itself, as well as data collection and integrity, were implemented (as detailed in the “Guidance for Site Documentation and Data Management Querying of Data Impacted by COVID-19” [GSD]).

The impact of COVID-19 on the statistical analysis is discussed in [Section 6](#) Subject Disposition, [Section 7](#) Protocol Deviations, [Section 11](#) Concomitant and Post-Treatment Medication, and [Section 14.1](#) Adverse Events.

4 ANALYSIS SETS

Randomized Analysis Set

The Randomized Analysis Set includes all randomized subjects. Subjects will be analyzed based on their randomized treatment assignment.

Safety Analysis Set

The Safety Analysis Set includes all randomized subjects who received at least one dose of study drug (ACP-044 or placebo). Subjects will be analyzed based on the treatment that they actually received. The Safety Analysis Set will be used for all safety analyses.

Full Analysis Set

The Full Analysis Set includes all randomized subjects who received at least one dose of study drug post operation and who have undergone bunionectomy. Subjects will be analyzed based on their randomized treatment assignment. The Full Analysis Set will be used for the analysis of all efficacy endpoints.

Per-protocol Analysis Set

The Per-protocol (PP) Analysis Set includes all subjects in the Full Analysis Set who did not have any protocol deviations that could potentially have a substantial impact on the primary efficacy outcome. The precise reasons for excluding subjects from the PP Analysis Set will be fully defined and documented in a separate PD log file prior to the clinical database lock. Subjects will be analyzed based on their randomized treatment assignment. The PP Analysis Set will be used for supportive analyses of the primary efficacy endpoint.

Pharmacokinetics Analysis Set

The Pharmacokinetics Analysis Set includes all subjects with at least one measurable ACP-044 plasma concentration.

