Visit Day	-28 to -2	Day -1 Predose	Day -1 (Dosing and Postdose)	Day 1 (Time 0)	Day 2	Day 3	Day 4 (EOT/ET)	Unscheduled Visit ^m	Clinic visit 7 days after EOT	Telephone call 30 days after last dose
Visit window (# days)		0	0	0	0	0	0		±3	+4
Informed consent	X									
Inclusion/exclusion criteria	X	X								
Medical and surgical history and demographics	X									
Physical examination	X	X					X^k		X^k	
Vital signs ^a	X	X		X	X	X	X	X		
Height, weight ^b	X	X								
12-lead ECG ^c	X	X		X	X	X	X			
Clinical laboratory tests	X	X					X			
Pregnancy test ^d	X	X								
Urine toxicology screen	X	X								
COVID-19 test ^e	X	X								
Clinic check in/out		X					X			
Randomization		X								
Study drug administration			X	X	X	X				
Pain assessment training ^f	X	X								
Bunionectomy			X							
Block Quality Assessment ^g			X							
11-point Numeric Rating Scale (NRS) of pain intensity ^h				X	X	X	X			
Foot and Ankle Ability Measure		X							X	
Rescue medication ⁱ				X	X	X	X			

Table S-1 Schedule of Events and Assessments for ACP-044-004 (Continued)

	Screening Period		F	Double-b Freatment						afety -up Period
Visit Day	-28 to -2	Day -1 Predose	Day -1 (Dosing and Postdose)	Day 1 (Time 0)	Day 2	Day 3	Day 4 (EOT/ET)	Unscheduled Visit ^m	Clinic visit 7 days after EOT	Telephone call 30 days after last dose
Visit window (# days)		0	0	0	0	0	0		±3	+4
Global evaluation of study drug				X	X	X	X			
C-SSRS	X	X					X			
PK blood sample collection ^j		X		X	X	X				
Issue diary							X ^l			
Collect diary									X	
Prior and concomitant medications	X	X	X	X	X	X	X	X	X	X
Assessment of adverse events	X	X	X	X	X	X	X	X	X	X

Abbreviations: AE=adverse event; COVID-19=Coronavirus disease 2019; C-SSRS=Columbia-Suicide Severity Rating Scale; ECG=electrocardiogram; EOT=end of treatment; ET=early termination; SAE=serious adverse event

- Vital signs will be evaluated starting at Screening; Day -1 predose and on Day 1 every 2 hours for the first 6 hours after the initial dose. Vital signs then to be evaluated every 6 hours thereafter until Day 4/end of treatment. A 15-minute window is permitted for vital sign measurements.
- b Height and BMI will only be measured and calculated at the Screening visit; weight will be measured at Screening and Day -1 predose.

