4.5.2 Handling of Subject Discontinuation During the Treatment Period

Unless the subject has withdrawn consent from all components of the study, every reasonable effort should be made to complete Day 4/EOT/ET and all safety follow-up assessments (as outlined in Table S–1) for all subjects who discontinue prematurely during the treatment period of the study. All information will be reported on the applicable pages of the electronic case report form (eCRF).

If a subject is discontinued from the study because of an AE, every reasonable attempt should be made to follow and appropriately treat (or refer for treatment) the subject until the AE resolves or until the Investigator deems the AE to be chronic or stable. For subjects who continue to be followed for safety, SAEs should continue to be reported as described in Section 7.4.2. All SAEs will continue to be followed and appropriately treated until such events have resolved or the Investigator deems them to be chronic or stable.

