6.4 Efficacy Assessments

6.4.1 Numeric Rating Scale of Pain Intensity

A 0 to 10 NRS will be used to assess the subject's pain at the time of popliteal and/or ankle nerve block removal, for the subsequent 72 hours, and for the 7 days after EOT. Subjects will be asked:

"Please describe your foot pain at the present time from 0 to 10 where "0" means "no pain at all" and "10" means "the worst pain imaginable".

Trained study coordinators will present the NRS scale and all other questionnaires at the designated times.

Pain (efficacy) assessments are to be recorded hourly (±15 minutes) for a 12-hour interval on Day 1 beginning immediately prior to the fifth dose (time 0) administered in the study. Pain assessments will continue every 3 hours during the subsequent 12 hour interval, and then every 6 hours thereafter until 72 hours, then once daily in the morning until the follow-up clinical visit. Pain assessments should also be obtained immediately prior to the administration of rescue medication.

Subjects should not have ice administered to the surgical area within the 30 minutes prior to each pain assessment. Pain assessments should be performed before blood sample collection, ECG, and other procedures.

Subjects will be provided a diary upon discharge to document their pain from EOT to the follow-up clinic visit that occurs 7 days after EOT.

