9.4 Subject Populations for Analysis

The **Safety Analysis Set** includes all randomized subjects who received at least one dose of study drug (ACP-044 or placebo). Subjects will be analyzed based on the treatment that they actually received. The Safety Analysis Set will be used for all safety analyses.

The **Full Analysis Set** includes all randomized subjects who received at least one dose of study drug and who have undergone bunionectomy with at least one postoperative pain assessment. The Full Analysis Set will be used for the analysis of all efficacy endpoints.

The **Per-protocol (PP) Analysis Set** will consist of those subjects in the FAS who did not have any protocol deviations that could potentially have a substantial impact on the primary efficacy outcome. The precise reasons for excluding subjects from the PP Analysis Set will be fully defined and documented prior to the clinical database lock. Subjects will be analyzed

Final Version: 1.0

supportive analyses of selected efficacy endpoints.

Clinical Study Protocol Amendment 5 Date: 01 February 2022 based on their randomized treatment assignment. The PP Analysis Set will be used for

For ACP-044 plasma concentration summaries, the **Pharmacokinetics Analysis Set** will consist of subjects with at least one measurable ACP-044 plasma concentration.

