1 INTRODUCTION

This statistical analysis plan (SAP) provides a technical and detailed elaboration of the statistical analyses of safety and efficacy data as described in the study protocol Version 1.0 amendment 5 dated 01 February 2022.

Specifications for tables, figures, and listings are contained in a separate document. Statistical analyses for population pharmacokinetic (PK) and PK/pharmacodynamics (PD) modeling will be presented in a separate report and therefore will not be included in this SAP.

This plan should be read in conjunction with the study protocol and the electronic case report forms (eCRF).

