The first dose of study drug will be administered within 60 (± 15) minutes prior to the start of surgery. Subjects will then have a popliteal and/or ankle nerve block administered to anesthetize the knee, distal leg, and foot, after which they will enter into surgery. Following surgery, subjects will be administered the remaining three daily doses approximately every 6 hours after the initial dose.

Day 1 is defined as the day after surgery. The popliteal and/or ankle nerve block will be discontinued approximately 2-4 hours prior to the first dose on Day 1 (i.e., the fifth dose of the study) and nerve block removal; a discontinuation window of approximately 2 hours is permitted. The time at which the first dose on Day 1 is administered will be time 0 for all pain assessments. Study drug administration and study procedures are to be completed on Days -1 through 4 according to the schedule of assessments ([Section 21.1](#)). Subjects will be encouraged to refrain from taking rescue medication until 1-2 hours following the first dose of study drug on Day 1.

[figure not shown]
On Day 4, after the 72 hour pain assessments are performed, the EOT procedures will be completed and subjects will be discharged from the clinical site.

Safety Follow-up Period

Safety will be further assessed during a follow-up visit to occur in the clinic approximately 7 (± 3) days after EOT/ET procedures and subjects will receive a follow-up telephone call approximately 30 (+4) days after the last dose of study drug. Subjects should return to standard of care after the follow-up visit that will occur in the clinic 7 (± 3) days after the EOT/ET.

The study schematic is presented in [Figure 1](#).

Figure 1 Schematic of Study Design

Abbreviations: EOT=end of treatment

^a Subjects to be randomized in a 1:1:1 ratio to receive either a once-daily oral dose of 1600 mg ACP-044, four oral doses of 400 mg ACP-044, or placebo. Randomization will occur just prior to surgery when the first dose of study drug is given.

^b The time at which the first dose on Day 1 (i.e., the fifth dose of study drug) is administered will be considered time 0 for pain assessments.

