19 CHANGES TO ANALYSES SPECIFIED IN PROTOCOL

None.

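### The protocol and the SAP define different Full Analysis Sets, by wording neither contains the other, and SAP Section 19 records no change

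*SAP*

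**What the plan says.** The SAP definition, in Section 4, reads: "The Full Analysis Set includes all randomized subjects who received at least one dose of study drug post operation and who have undergone bunionectomy". It has no pain-assessment condition.

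The protocol definition, in Section 9.4 and again in the synopsis, counts any dose and limits the set to subjects "who have undergone bunionectomy with at least one postoperative pain assessment". Neither document says which assessment qualifies.

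Both documents use this set for every efficacy endpoint. It carries the primary ANOVA (SAP 13.1.1) and all key secondary tests (SAP 13.2).

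On timing, the first dose is given before the nerve block and surgery. Then: "Following surgery, subjects will be administered the remaining three daily doses approximately every 6 hours after the initial dose". The fifth dose, the first on Day 1, defines time 0 for pain assessment.

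SAP Section 1 presents the plan as an elaboration of the analyses "as described in the study protocol Version 1.0 amendment 5 dated 01 February 2022". The only entry under SAP Section 19, "CHANGES TO ANALYSES SPECIFIED IN PROTOCOL", is that there are none.

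**The concern.** Protocol 9.1 leaves statistical detail to the SAP, so a fuller definition there would be normal. But Protocol 9.4 states the FAS in full and defers only the reasons for per-protocol exclusion. The SAP adds one condition (a dose after surgery) and removes another (a pain assessment). That is a change to amendment 5, and the section meant to record such changes says there are none.

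Three things are at stake.

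- **Pre-specification.** Two written definitions exist for the set behind the confirmatory tests, with no statement of which prevails.
- **Selection.** Both definitions condition on events after randomization. The SAP's dose condition also removes anyone who stops for an adverse event or lack of efficacy between surgery and dose 2. The estimand's worst-pain rule for such stops (SAP 13.1.1) would otherwise apply to them.
- **No check.** The sensitivity analyses in SAP 13.1.2 vary rescue handling and imputation, not the analysis set. The optional per-protocol run (SAP 13.1.3) uses a subset of the FAS.

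**Working it through.** **1. The definitions side by side.** Take subjects who had the pre-operative dose and surgery.

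| Post-operative dose | Postoperative pain assessment | Protocol FAS | SAP FAS |
|---|---|---|---|
| yes | yes | in | in |
| no | yes | in | out |
| yes | no | out | in |
| no | no | out | out |

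The second and third rows show that neither set contains the other.

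**2. Which rows are likely to have members.** This depends on the undefined term.

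- *NRS from block removal or time 0 (the natural reading).* Protocol 6.4.1 has the NRS assess "pain at the time of popliteal and/or ankle nerve block removal, for the subsequent 72 hours", and starts the efficacy series just before the fifth dose. Doses 2-4 normally come earlier, so row two is nearly empty. Row three holds those who take one of doses 2-4 and leave before any NRS.
- *NRS at early termination also counts.* Table S-1 marks the row "11-point Numeric Rating Scale (NRS) of pain intensity" in the Day 4 (EOT/ET) column. For subjects who stop early, Protocol 4.5.2 says "every reasonable effort should be made to complete Day 4/EOT/ET and all safety follow-up assessments", unless consent is fully withdrawn. Stops before dose 2 with such a visit then fall in row two, and row three shrinks.
- *The pain item of the hourly block assessment counts (Protocol 6.3, SAP 6.1).* Row two is those who stop after surgery and before dose 2. Row three is nearly empty.

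**3. The plan's own figures.** Inputs from SAP 3.5: difference 23, SD 50, 76 per arm, two-sided 0.05, t-test, at most 5% excluded.

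- Power at 76 per arm is 80.4%, and 76/0.95 = 80. Both reproduce.
- The 5% allowance is 0.05 × 80 = 4 subjects per arm, for any reason.
- SE of a difference = 50 × √(2/76) = 8.1.
- Losing two more per arm (74) gives 79.4% power, a cost of about 1 percentage point.

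**4. Shift in an arm mean.** The documents give no count of affected subjects. Assume k = 1 or 2 adverse-event or lack-of-efficacy stops, all in one arm of 80. If each is imputed d points above the mean of the other subjects in the arm, including rather than excluding them shifts the arm mean by k × d / 80.

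The value of d comes from simulating Appendix 21.2, steps 6-8, with these assumptions:

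- 76 completers, the 17 NRS times from 0 to 24 h, integer scores 0-10;
- between-subject SD 2.1; autoregressive within-subject SD 1, 1.5 or 2; hourly correlation 0.7 or 0.9;
- arm mean AUC about 97, 120 or 143. The resulting AUC SD was 49-56, against the planned 50;
- the dropout starts from the arm mean at time 0, as SAP 5.2.1 prescribes. Site terms are omitted.

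| Rescue handling | d | Smallest shift (k = 1) | Largest shift (k = 2) |
|---|---|---|---|
| 4-hour replacement as in the SAP, rescue assumed at NRS ≥5 | 27-70 | 27/80 = 0.34 | 2 × 70/80 = 1.75 |
| No replacement | 36-95 | 36/80 = 0.45 | 2 × 95/80 = 2.4 |

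The largest shift with replacement is 1.75/23 = 8% of the planned difference and 1.75/8.1 = 0.22 SE. Without replacement it is 2.4/23 = 10% and 2.4/8.1 = 0.30 SE.

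Withdrawals for other reasons are imputed within their own arm. There, d was between -9 and +4 without rescue replacement, so the shift is at most 2 × 9/80 = 0.2 points.

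**5. Time 0.** SAP 3.1 and 5.2.2 tie time 0 to the first Day 1 dose. A subject with one of doses 2-4 but no fifth dose is in the current SAP set and has no defined time 0.

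**The case against.** The strongest reply is that this is a documentation slip with almost no practical effect. Several parts of it stand.

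- **The term is less open than a list of candidates suggests.** Table S-1 keeps the block assessment in a separate row, and SAP 6.1 reports it with baseline characteristics. A reader might infer that the two sets diverge widely in both directions. On the natural reading the protocol-only group is nearly empty, so in practice the SAP set almost contains the protocol set.
- **Early stops are not invisible.** A reader might infer that an imbalance between arms would go untabulated. SAP Section 7 refutes this: it summarizes early discontinuation by reason and treatment group in the Randomized Analysis Set, and tabulates subject counts by analysis set and treatment group. Only a table of FAS exclusions by reason is lacking; those are listed per subject.
- **The SAP wording is not simply worse.** Both definitions use post-randomization events, and the SAP dropped a condition on having outcome data, which is a gain. Counting the block item as a qualifying assessment would be a preference, not a correction.
- **The exposed window before dose 2 is short.** It ends about 6 hours after dose 1, in inpatients with observed dosing and the block in place.
- **Nothing suggests concealment.** The SAP definition is stated openly in Section 4.

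None of this removes the contradiction between the two definitions or makes the Section 19 entry correct.

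**Conclusion.** The point holds as a pre-specification defect that should be corrected before unblinding. The two definitions contradict each other, the difference is more than elaboration, and the SAP's statement of no changes is wrong for the set that carries the primary and key secondary tests.

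The numerical consequence is probably small: about 0.3-1.8 AUC points in one arm's mean with rescue replacement, and up to about 2.4 without it. That range rests on an assumed one or two adverse-event or lack-of-efficacy stops, all in the same arm, on the simulated score distributions, and on the assumed rescue threshold. If the stops are balanced between arms, the bias is about zero. The documents do not support a claim of material bias or of a meaningful loss of power, and the sample size does not need to change.

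**What to change.** Before unblinding:

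1. State one FAS definition in both documents, preferably without the post-operative-dose condition. If a pain-assessment condition is kept, name the assessments that qualify. Record the change and its reason in SAP Section 19.
2. If membership differs, repeat the primary ANOVA in the definition not adopted, or in both current definitions if neither is adopted. Add FAS exclusions to the existing SAP Section 7 table of per-protocol exclusions by reason and arm.
3. State the analysis time 0 for FAS subjects who never receive the fifth dose, for example its scheduled clock time.

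The cost is a wording change, a Section 19 entry, an extended table and normally one extra run of the primary analysis (two if neither current definition is adopted). No new data are needed. The downside is that a few subjects would rest on imputed values starting from a same-arm mean at time 0. The current SAP set already admits such subjects.

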5 DATA HANDLING CONVENTIONS

5.1 General Data Reporting Conventions

Continuous variables will be summarized using the following descriptive statistics: number of subjects, mean, median, standard deviation (SD), standard error (SE), minimum, and maximum. Unless specified otherwise, means, medians, and confidence intervals (CIs) will be presented to one more decimal place than the raw data, and the standard deviations and standard errors will be presented to two more decimal places than the raw data. In general, the maximum number of decimal places is 4 and values will be truncated to 4 decimal places in situations where there are more than 4 decimal places. Wherever possible data will be decimal aligned.

Categorical variables will be summarized by the number of subjects and the percent of subjects in each category; the number of subjects and the percentage of subjects with missing data will be summarized for demographic and baseline characteristics (if applicable).

Categories with zero counts will not have zero percentages displayed. For demographic summaries, percentages will be calculated by using the total number of subjects in the given treatment group as the denominator. Percentages will be presented with one decimal place.

Unless specified otherwise, all statistical hypothesis tests will be 2-sided and performed at the significance level of 5% for treatment comparisons and all CIs will be 2-sided 95% CIs. P-values will generally be presented to 4 decimal places; values less than 0.0001 will be presented as <0.0001.

Values that are collected with “<” or “>” signs will generally be analyzed as the numerical value without the sign in tables and figures. In listings, these data will be reported as collected with the sign.

5.2 Derived Variables

In general, the assessment scale scores will be directly taken from the electronic case report form (eCRF), the variables of mean area under the curve values will be derived and used for all analyses.

 - Multiple imputation will be used to impute values at the scheduled assessment times for subjects that discontinue. For the purposes of imputation, unscheduled values and pre-rescue values will not be included, but will be added back into the dataset prior to calculating the AUC; however, scheduled values will be replaced with pre-rescue values during the censoring period prior to the imputation (and solely for the purpose of imputation). First, subjects that discontinue for reasons other than lack of efficacy (LOE) and

adverse events (AEs) will have their values imputed within treatment group with MI assuming MAR with covariates for all observed time points. For subjects who discontinue due to AEs or LOE, the MI will be based off the distribution of worst values through the time of discontinuation. This will be done iteratively for each time point starting at the earliest time point with missing data; covariates will be included for observed data through that time point. Full details of the MI algorithm are given in [Appendix 21.2](#).

In general, the area under the curve (AUC) from start time of interest, t_{start} , to end time of interest, t_k , for each subject will be calculated using the linear trapezoidal method. All pain assessments (including unscheduled) will be used in the calculation.

$$AUC_{t_{start}-t_k} = \sum_{i=start}^{k-1} \frac{1}{2} * (Pain_i + Pain_{i+1}) * (t_{i+1} - t_i)$$

Where i indexes the timepoints from 0 hour to 72 hours as 0 to 24; $start$ is the index value of the starting time; k is the index value of the end time; t_{start} is the start time of the AUC to be calculated; t_k is the end time of the AUC to be calculated; $Pain_i$ is the NRS pain intensity score at index i ; t_i is the time at index i . **Note:** The index count will be adjusted on an individual basis to account for unscheduled assessments and pre-rescue assessments. Calculations will be performed at a 1-minute precision, but final values will be scaled to hours, thus the AUC_{0-24} will be scaled 0-240.

For the primary efficacy endpoint the formula would be as follows:

$$AUC_{0-24} = \sum_{i=0}^{16-1} \frac{1}{2} * (Pain_i + Pain_{i+1}) * (t_{i+1} - t_i)$$

Note: The index count will be adjusted to account for unscheduled assessments.

